The primary endpoints will be the between group difference in change of dizziness related handicap and preferred gait velocity from baseline to 6 and 12 months follow up.

The study has two primary outcomes:

Dizziness-related handicap is measured using the Dizziness Handicap Inventory (DHI). The DHI is designed to quantify the perceived impact of dizziness and unsteadiness. It contains 25 questions, each item has 3 alternative scores “0” (no), “2” (sometimes) and “4” (yes), giving a score range of 0 to 100 DHI points (8).

Preferred gait velocity is used as a measure of functional level. The participants are asked to walk down an 8-meter pathway, timed in the middle 6 meters. The trial is timed using a stopwatch, from when the first foot passes the start point, to where the last foot passes the stop point. The mean velocity over two trials is calculated and presented in m/s.

A more detailed description of the study is presented in the protocol (1).

10. Randomisation and blinding.

After BI-VR the participants were block-randomised (in blocks of 16) into two groups, the CONTROL or TREATMENT group (Group A or B). Group allocations were performed using a random number generator and presented in a concealed envelope after completing the BI-VR. After breaking the code, the BI-VR therapist and the participants were aware of group allocation, while the assessor, also analysing the data, remained blinded. Prior to testing at 6- and 12-months participants were reminded not to divulge group allocation.

Prior to breaking the blinding, the authors of this SAP will agree on how to interpret the results on the bases of a blinded review of the data from the primary endpoints. Two possible interpretations will be made. One assuming that group A was in the treatment group, and the other assuming that group B was in the treatment group. When all authors have agreed to the interpretations, the randomisation code may be open. This procedure is conducted to reduce bias in the interpretation of the results.

11. Sample size calculation

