The sample size calculation was based on the between group difference in the mean change scores of the total DHI score and the preferred gait velocity. As two primary outcomes were chosen for the study power and sample size calculation was calculated for both outcomes (1). In order to obtain a clinically important group difference in the DHI of 11 points (9), with a significance level of 0.05 and a power of 80% (SD 18.95), 47 participants are required per group. In order to obtain a clinically important group difference in preferred gait velocity of 0.1 m/s (10, 11) with a significance level of 0.05 and a power of 80% (SD 0.15), 36 participants are required per group.

Therefore, the larger sample size of 47 in each group was used, resulting in at least 94 participants. To reduce the risk of dropouts affecting the analyses the preferred sample size was set to 124 participants, allowing for a conservatively estimated drop-out rate of 24%.

12. Description of hypothesis testing framework

All outcomes will be analyzed using a superiority framework, expecting that participants attending TREATMENT group will improve more than participants in the CONTROL group.

13. Planned interim analyses and stopping guidance

The published study protocol suggested possible interim analyses to adjust sample size. Apart from that no formal stopping guidelines or interim analyses were planned.

14. Details of timing of analyses

Participants were assessed at baseline, with follow-up testing after approximately 6 and 12 months. All analysis will be analysed after final data-collection. The primary outcomes will be analysed by a blinded biostatistician. The secondary outcomes will be analysed by LK. Data from baseline, 6- and 12-months follow-up will be included in these analyses. All primary and selected secondary outcomes presented at www.clinicaltrials.gov (NCT02655575) will be presented in the primary or subsequently secondary reports.

15. Timing of outcome assessments

Table 1. An overview of the different stages of the study, with a presentation of outcomes and their timepoint for testing.

Timepoint	STUDY PERIOD			
	Enrolment	Post-allocation		
	Month 0-2	Month 1-6	6 months	12 months
ENROLMENT				
Eligibility screen	X			
Informed consent	X			
Allocation		X		
INTERVENTIONS				
BI-VR		X		
VR-CBT/ Home exercises			X	
ASSESSMENTS				
Initial questionnaire and demographics	X			
Clinical dynamic visual acuity	X			
Grip strength	X			
PRIMARY OUTCOMES				

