Intention-To-Treat: Primary analyses will be conducted according to intention to treat protocol, where all participants were included according to the treatment group they were randomized into. The distribution of the primary outcomes (change score of DHI and preferred gait velocity) will be visualized using scatterplots and described by mean and 95% CI for each group.

Per protocol: In addition, analyses will be conducted on the two groups with respect to treatment adherence (See definition of good adherence section 19a). Thus, analyses will be conducted using per protocol analysis, according to this comparison:

- Participants in the CONTROL group with good adherence, and no other interventions.
- Participants in the TREATMENT groups with good adherence, and no other interventions.

SECTION 5: TRIAL POPULATION

Screening data

- 21. Reporting of screening data

The total number of possible participants screened for eligibility throughout the recruitment period (start and end date) will be reported.

Eligibility

- 22. Summary of eligibility criteria

Inclusion criteria:

- 18-70 years
- Acute onset of dizziness, with symptoms lasting at least 3 months
- Dizziness triggered/ worsened by head movements

Exclusion criteria:

- Self-reported non-vestibular reason for dizziness (e.g. neurological condition)
- Fluctuating vestibular disease (e.g. Menière's disease)
- Recently treated or organised future treatment for benign paroxysmal positional vertigo (1 month previously or in the future).
- Conditions where fast head movements are contraindicated (e.g. osteoporosis of the neck)
- Severe/ terminal pathology
- Participation of group therapy for dizziness in within the past year

- Inadequate Norwegian language proficiency (written and oral)
- Unable to attend test and treatment location.

Recruitment and withdrawals

- 23 & 24: Information to be included in the CONSORT flow diagram

The CONSORT flow diagram will consist of the following:

- All patients assessed for eligibility throughout the recruitment period
- All patients meeting one or more of the exclusion criteria, with reasons
- All patients eligible for inclusion in the trial
- All eligible patients not consenting, with reasons
- All patients randomized for both treatment arms
- All patients receiving and not receiving the allocated treatment for both treatment arms
- All patients with answered DHI questionnaire at 6- and 12-months follow-up

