- All patients with registered preferred gait velocity at 6- and 12-months follow-up
- Withdrawals/lost to follow-up with reasons and timing for both treatment arms
- Patients included in the ITT and per protocol for both treatment arms

Baseline patient characteristics

- 25a: List of baseline characteristics to be summarized

Baseline data that will be presented include: Age, gender, duration of dizziness, education level, reported employment status, number of dizziness complaints, reported weekly activity level. In addition will primary and secondary outcome scores at baseline be presented.

For further details, please see the published study protocol (1).

- 25b: Details on descriptive summary of baseline characteristics

Categorical and binary data will be summarized by absolute and relative frequencies. Continuous and count data will be summarized by mean and median with standard deviation and percentiles as appropriate. In case of only few different values observed or unusual shape of the distribution (e.g. bimodality, extreme skewness), also absolute and relative frequencies will be reported, potentially after a suitable categorization. No formal tests for significant differences between groups at baseline will be performed, as this is not recommended by CONSORT.

SECTION 6. ANALYSIS

Outcome definitions

- 26. Specification of outcomes and timing.

Table 1 presents an overview of the outcomes and timing. A detailed presentation of the primary outcomes is presented in section 3, while the secondary outcomes are presented in the study protocol (1).

Analysis methods

- 27. What analysis methods will be used

All outcomes will be presented using descriptive statistics; normally distributed data by the mean and standard deviation (SD), and skewed distributions by median and interquartile range (IQR). Binary and categorical data will be presented using *counts* and percentages.

Primary outcomes:

The efficacy analysis will be based on the assessment of the between group differences in changes in DHI scores and preferred gait velocity at 6- and 12-month follow-up. A linear-mixed model with repeated measures will be applied, where group allocation (TREATMENT and CONTROL) and time (6 and 12 months) will be treated as categorical values. The estimated difference in change will be presented in group means and 95% confidence intervals with associated p-values.

Secondary outcomes

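### The primary mixed model gives measured baseline values no covariate role and states no group-by-time term, losing precision and leaving the 6- and 12-month effects unspecified

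*Combined protocol and SAP*

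**What the plan says.** Section 9 defines the primary endpoints as the "between group difference in change of dizziness related handicap and preferred gait velocity from baseline to 6 and 12 months follow up". Section 27 repeats that target, "between group differences in changes in DHI scores and preferred gait velocity at 6- and 12-month follow-up", and then gives the type of model: "A linear-mixed model with repeated measures will be applied". The only terms it names are two factors, in the clause "where group allocation (TREATMENT and CONTROL) and time (6 and 12 months) will be treated as categorical values". The output is described in one sentence: "The estimated difference in change will be presented in group means and 95% confidence intervals with associated p-values".

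Section 27 mentions no baseline covariate, no group-by-time interaction and no covariance structure. Its time factor has two levels, and baseline is not one of them.

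Two other places bear on how to read it. Section 20 identifies the primary outcomes as change scores: "The distribution of the primary outcomes (change score of DHI and preferred gait velocity) will be visualized using scatterplots". Section 14 says "Data from baseline, 6- and 12-months follow-up will be included in these analyses" but does not say in what role baseline enters. Table 1 schedules both primary outcomes at baseline, 6 and 12 months. Section 17 applies Holm-Bonferroni to the two primary outcomes. Section 27 also sends the continuous secondary outcomes through the same method.

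**The concern.** The natural reading of Sections 20 and 27 together is a model of change from baseline at two visits, with group and time as the only terms. This has two consequences.

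First, a change score subtracts the whole baseline value, when the best linear use of it subtracts only the part that predicts follow-up. Under equal variances, the variance is larger than with baseline adjustment at any correlation below 1. The data needed to recover that precision are already collected.

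Second, group plus time without an interaction assumes the same treatment effect at both visits. The VR-CBT programme lasts 8 weeks, so an effect that fades or builds between 6 and 12 months is plausible, and it would be averaged away. The endpoint is stated at both visits, so the analyst would have to add a term that the SAP does not name. Nor is it clear which p-value for each outcome goes into the Holm procedure.

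**Working it through.** **Inputs.** From Section 11: DHI difference 11 points, SD 18.95, 47 per group; gait difference 0.1 m/s, SD 0.15, 36 per group; alpha 0.05, power 80%. Section 16: two-sided tests. Not in the documents, so assumed: equal variances at all visits, complete data, and baseline/follow-up correlation r. The main range is r = 0.5 to 0.7, widened below. 18.95 is read as the SD of change, because Section 11 says the calculation rests on mean change scores. Normal approximation throughout.

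**The plan's own figures.** n = 2 × [SD × (1.960 + 0.842) / difference]².
- DHI: 46.6, so 47 per group.
- Gait velocity: 35.3, so 36 per group.
- Dropout: 94 / (1 − 0.24) = 123.7, so 124.

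All are reproduced.

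**Single visit.** With variance σ² at each visit, Var(change) = 2σ²(1 − r) and Var(follow-up given baseline) = σ²(1 − r²). The ratio is (1 + r)/2.

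The standard error of the unadjusted DHI contrast is 18.95 × √(2/47) = 3.91, so the standardised effect is 11/3.91 = 2.814. Power = Φ(2.814/√ratio − 1.960). Without adjustment it is 80.3%.

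**Two-visit average.** Assume the same correlation r between all three visits. The average of the two changes has variance 1.5σ²(1 − r), which is 0.75 of the single-visit figure. The standardised effect is 2.814/√0.75 = 3.249, and unadjusted power is Φ(3.249 − 1.960) = 90%. With baseline adjustment the variance is σ²(1 − r)(1 + 2r)/2, a ratio of (1 + 2r)/3 to the unadjusted average.

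| r | Single-visit ratio | Single-visit power, adjusted | Two-visit ratio | Two-visit power, adjusted |
|---|---|---|---|---|
| 0.5 | 0.75 | 90.1% | 0.67 | 98% |
| 0.6 | 0.80 | 88.2% | 0.73 | 97% |
| 0.7 | 0.85 | 86.3% | 0.80 | 95% |
| unadjusted | 1 | 80.3% | 1 | 90% |

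For 80% power at a single visit, the DHI would need 35, 38 and 40 per group at r = 0.5, 0.6 and 0.7 instead of 47. Gait velocity would need 27, 29 and 31 instead of 36.

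**Sensitivity.** At r = 0.3 and 0.8, adjusted single-visit power is 93.7% and 84.3%. If 18.95 is instead the SD of a single score, the SD is 18.95 × √(2(1 − r)) for change and 18.95 × √(1 − r²) after adjustment. Power then goes from 66% to 84% at r = 0.3, from 80% to 90% at r = 0.5, and from 95% to 98% at r = 0.7. The gain persists, but its size depends on inputs that the documents do not give.

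**Group plus time, fitted literally.** On change scores with both visits weighted equally, the group coefficient is the mean of the two visit effects:
- true effects 11 and 0: (11 + 0)/2 = 5.5;
- true effects 11 and 5.5: 8.25;
- true effects 8 and 14: 11.

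If Section 14 meant baseline as a third response level, still without an interaction, a constant effect of 11 would be returned as (0 + 11 + 11)/3 = 7.33. With the interaction but no constraint on baseline means, that layout returns the raw change contrast. Each reading gives a different estimate or precision, and the SAP does not say which one applies.

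**The case against.** The strongest reply is that the SAP is silent on the interaction and does not rule it out. The clause in Section 27 says how two variables are coded; it need not be a complete list of terms. The stated target, differences in change at each follow-up, implies visit-specific effects. This stands. A reader might infer that the planned model cannot deliver the 6- and 12-month effects, but that is true only of a literal additive fit. Section 27 also leans on a published protocol that is not among the documents, so it cannot be checked whether the terms are given there.

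Second, analysing change is legitimate and matches the basis of the sample size. Randomisation keeps the contrast unbiased on average, and the trial is not underpowered on its own inputs. This stands too. It may be tempting to count chance baseline imbalance as a separate harm. At r = 0.6, σ = 18.95/√0.8 = 21.2, a one-standard-error imbalance is 21.2 × √(2/47) = 4.4 points, and it moves the change contrast by (1 − 0.6) × 4.4, about 1.7 points. That is under half the standard error of 3.91, which already includes this variation. It is the mechanism of the precision loss, not a further bias.

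Third, the 80% starting point belongs to a single visit; a literal group-plus-time fit pools two visits and starts near 90%. That is right, so both scales are shown. Similarly, testing the DHI at 0.025 gives Φ(2.814 − 2.241) = 72%, but this is a Bonferroni floor. Holm tests the second outcome at 0.05 once the first is rejected, so 72% is not the trial's power under its own procedure.

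Fourth, reporting contrasts at two visits for two outcomes adds estimates without saying which are confirmatory. This also stands, and the fix has to deal with it. None of these points removes the gain from using baseline as a covariate.

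**Conclusion.** The point holds as a matter of efficiency and specification. As written, the SAP analyses unadjusted change and leaves measured baseline values without a covariate role. Under equal variances, 18.95 as the SD of change and r between 0.5 and 0.7, this forgoes a 15 to 25% reduction in single-visit variance (80% power against 86-90%), or 20 to 33% for a two-visit average under equal correlations (90% against 95-98%). The direction holds for any r below 1 under equal variances; the size rests on a correlation that the documents do not supply.

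The interaction is unspecified, not excluded. If it is left out, the analysis reports one averaged effect in place of the two that the endpoint names. The documents do not support a claim that the plan is biased, invalid or underpowered. The change should be made, but the trial does not fail without it.

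**What to change.** In Section 27, state the primary model for each outcome as follow-up value (or change) on arm, time, arm × time, baseline value and baseline × time, with the within-participant correlation structure named. A constrained model, with baseline as a level of time and a common baseline mean in the two arms, would serve the same purpose. Say which is used, and bring Sections 14 and 20 into line on the role of baseline.

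Report the arm difference at 6 and at 12 months with confidence intervals. Name the one contrast per outcome that enters the Holm procedure in Section 17, and label the rest as supportive. Settle this before the Group A/Group B code is opened, and preferably before the blinded results are shown to the authors, so that the choice cannot follow the data. Use the same model for continuous secondary outcomes that have a baseline; Table 1 shows none for Patient Global Impression of Change.

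The cost is a few sentences of SAP text and no new data. The one decision it forces is the choice of confirmatory contrast, which the present text also leaves open.

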Continuous secondary outcomes will be analyzed using the same method as described above.

Missing data

- 28. Handling of missing data

The analysis will use the Intention to Treat (ITT) principle, analysing all randomised participants independent of compliance and withdrawals. In the event of missing data two methods will be used.

For missing single questions, the mean baseline value for the respected group will be assigned. If a complete questionnaire or physical outcome is missing a non-responder imputation will be used.

Loss to follow-up analyses: Dropouts are defined as those who did not complete both physical assessment and patient reported outcomes at 6- or 12-month follow-up. Multiple imputation will be utilised where data is missing.

Additional analysis

- 29. Details of any additional analysis

Additional reports may be presented on the outcomes presented at ClinicalTrials.gov (ID: NCT02655575).

Harms

- 30. Handling of adverse events

Participants may experience increased symptoms in the short term. However, serious adverse events (e.g. death, life-threatening events, disability, and permanent damage) is not anticipated. We will report the number of adverse events if present.

Statistical software

- 31. Details of statistical package used for the analysis

STATA (StataCorp, College Station, Tx, USA) will be used for the analyses.

Operation procedures

- 32. Data management

Three assessors are involved in data collection. The principal investigator will register all data into files stored on a secure server. Paper copies, where applicable, will be stored securely, only accessible by the principal investigator. Personal information will be stored separate from the main data and will not be shared by anyone outside the central study team.

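### As written, a DHI item left blank at follow-up is filled with the arm's baseline mean, which on average shrinks the group difference in proportion to the share of items missing

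*Combined protocol and SAP*

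**What the plan says.** Section 28 (Handling of missing data) opens with "In the event of missing data two methods will be used". The first method is for items: "For missing single questions, the mean baseline value for the respected group will be assigned". The second is for a whole instrument or test: "If a complete questionnaire or physical outcome is missing a non-responder imputation will be used". A later paragraph on loss to follow-up adds "Multiple imputation will be utilised where data is missing" and does not say how this relates to the two methods before it.

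Neither method is tied to a visit. Table 1 schedules the DHI at baseline, 6 months and 12 months, and section 14 confirms that "Data from baseline, 6- and 12-months follow-up will be included in these analyses". The primary endpoint (section 9) is the "between group difference in change of dizziness related handicap and preferred gait velocity from baseline to 6 and 12 months follow up". On the structure of the DHI, section 9 says "It contains 25 questions, each item has 3 alternative scores"; the scores are 0, 2 and 4, so the total runs from 0 to 100.

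**The concern.** A change score needs a post-treatment value at follow-up. The item rule supplies a pre-treatment one instead, and takes it from the arm average although the same participant's remaining answers at that visit are on the form and tell more. The filled item therefore carries none of the improvement since baseline. On average this moves each arm's follow-up mean back toward its baseline mean, by more points in the arm that changes more, so the estimated difference between arms is reduced.

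At stake are some bias toward no difference in a primary outcome and some loss of power in a superiority trial. The rule is written for questionnaires in general, so the questionnaire-based secondary outcomes inherit it, and in a short scale one item carries more of the total. Preferred gait velocity has no items and is untouched.

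**Working it through.** **Inputs from section 11 and section 16.** DHI difference 11 points, SD 18.95, 80% power, 47 per group, 124 in total (62 per group); two-sided 5% level.

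**Reproducing the plan's figure.** n per group = 2 × (1.960 + 0.842)² × 18.95² / 11² = 46.6, rounded up to 47. This agrees with section 11. Power at n = 47, by the normal approximation: standard error = 18.95 × √(2/47) = 3.909; 11/3.909 − 1.960 = 0.854; Φ(0.854) = 80.3%. The sample size is not in dispute.

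**Effect of the item rule.** Let an arm's mean DHI total be B at baseline and F at follow-up, and let a share f of follow-up items be missing at random.

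- Expected follow-up total after filling: (1 − f)F + fB.
- Expected change: (1 − f)F + fB − B = (1 − f)(F − B).
- Between-group difference, with the same f in both arms: (1 − f) × true difference. The loss is f × 11 points at the design difference.

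**Numbers.** The documents give no item-level missing rate, so f is an assumed range. Power = Φ(difference / (18.95 × √(2/n)) − 1.960), with the SD held at 18.95. The column for 62 per group assumes no dropout.

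| f (assumed) | Expected difference | Loss | Power, 47 per group | Power, 62 per group |
|---|---|---|---|---|
| 0 | 11.00 | 0 | 80.3% | 89.8% |
| 1% | 10.89 | 0.11 | 79.6% | 89.2% |
| 2% | 10.78 | 0.22 | 78.7% | 88.6% |
| 5% | 10.45 | 0.55 | 76.2% | 86.7% |
| 10% | 9.90 | 1.10 | 71.7% | 82.9% |
| 20% | 8.80 | 2.20 | 61.5% | 73.4% |

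**Check by simulation.** The set-up was 25 items scored 0/2/4, 47 per arm, 600 replicates and invented item parameters. Each blank follow-up item was filled with the arm's baseline mean for that item. Differences under the SAP rule, against the same data complete:

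- f = 2%: −10.29 against −10.48 (ratio 0.98)
- f = 5%: −10.00 against −10.53 (ratio 0.95)
- f = 10%: −9.31 against −10.35 (ratio 0.90)

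At f = 10% the change within each arm shrank by about the same factor (−15.9 against −17.7, and −6.6 against −7.3). Filling from the same person's answered items at the same visit, also at f = 10%, gave −10.59 against −10.62, which is essentially unbiased.

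**The case against.** **The effect may be small.** At 1% to 5% missing items the loss is 0.11 to 0.55 DHI points, and with 62 per group and no dropout power stays at 86.7% or above. Nothing in the documents points to heavy item non-response. This stands, and it limits the severity. It does not rescue the rule, because the plan does not bound the rate.

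**The rule may be meant for baseline items only.** The text does not say so. If that was the intention, the plan has no item rule for follow-up and section 28 still needs rewriting.

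**Multiple imputation may cover it.** That sentence belongs to the loss-to-follow-up paragraph and does not withdraw the item rule.

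**The error is conservative in a superiority trial.** With random missingness at the same rate in both arms this is true: a real effect is reduced and none is created. With unequal rates, or with missingness related to severity, the direction is not guaranteed.

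Some stronger readings are tempting, and the documents do not support them:

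- *Five blanks would cost 29% of the target.* Assume a DHI of 45 at baseline and 29 at follow-up in the treatment arm. Five blanks then add 5 × (45/25 − 29/25) = 3.2 points, and 3.2/11 = 29%. But 3.2 points is one participant's scoring error, while 11 points is a difference between group means. If every participant in both arms left five of 25 blank (f = 20%), the loss would be 0.20 × 11 = 2.2 points, or 20%. Nor does a 7-point error in one much-recovered participant, 5 × (1.8 − 0.4) for a DHI of 10, measure the trial estimate.
- *Every filled item pulls that person back to the pre-treatment level.* The filled value is the arm's mean, not the person's own baseline. With an arm baseline mean of 45 (1.8 per item), someone at 70 (2.8 per item) at both visits who skips one follow-up item gets 1.8 for it, an apparent improvement.
- *The plan would fill a nearly empty form with baseline means.* Section 28 speaks of single questions and, separately, of a complete questionnaire. A mostly blank form falls between the two and is undefined. That is a gap in the wording, not a stated intention.

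**Conclusion.** The concern holds. Followed as written, the item rule puts pre-treatment arm means into post-treatment DHI totals and on average multiplies the between-group difference by (1 − f). At the design difference the loss is f × 11 points: 0.11 at 1%, 0.55 at 5% and 1.10 at 10%, with power at 47 per group of 79.6%, 76.2% and 71.7% against 80.3%.

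This rests on four assumptions: the rule reaches follow-up items (read from its unrestricted wording); the group it refers to is the participant's own arm; items are missing at random at the same rate in both arms; and the SD is unchanged. The value of f is assumed throughout.

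This should be fixed, but the documents do not show that it would overturn the primary result. A reader might infer a large distortion of the DHI result; that would need a high share of missing items, for which the documents give no evidence.

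**What to change.** Replace the item rule in section 28 with proration within the same person, questionnaire and visit: total = mean of the answered items × number of items in the instrument, provided a pre-specified minimum share is answered. A minimum of 80% (20 of 25 for the DHI) is one workable choice; the documents do not dictate the figure, and the sponsor may set another in advance. Where an instrument has its own scoring rule for missing items, use that instead.

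Below the minimum, treat the questionnaire as missing at that visit and handle it by the single method the SAP states for a missing questionnaire. The new threshold should not silently change that method. Section 28 names non-responder imputation for a missing questionnaire and then mentions multiple imputation, so the text should say which of them applies here.

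The cost is a few sentences in the SAP and a line of scoring code, with no new data collection. The change should be made before the group code is broken.

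### Section 28 fills a wholly missing DHI or gait visit by non-responder imputation, undefined for a continuous change, and also names multiple imputation for overlapping data without saying which is primary

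*Combined protocol and SAP*

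**What the plan says.** Section 28 commits to ITT, "analysing all randomised participants independent of compliance and withdrawals", and continues: "In the event of missing data two methods will be used". Two methods follow at once. For items: "For missing single questions, the mean baseline value for the respected group will be assigned". For whole assessments: "If a complete questionnaire or physical outcome is missing a non-responder imputation will be used".

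A further paragraph, labelled *Loss to follow-up analyses*, adds a third method. It gives a definition, "Dropouts are defined as those who did not complete both physical assessment and patient reported outcomes at 6- or 12-month follow-up", and then says: "Multiple imputation will be utilised where data is missing". It gives no imputation model, no predictors and no number of imputations, and nothing limits the method to a sensitivity analysis.

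Section 27 sets the primary analysis of change in DHI and gait velocity: "A linear-mixed model with repeated measures will be applied", with group and time (6 and 12 months) as categorical terms. It does not mention imputation. Section 27 applies the same method to the continuous secondary outcomes. Section 11 sets the total at 124 participants, "allowing for a conservatively estimated drop-out rate of 24" per cent.

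**The concern.** Non-responder imputation belongs to binary outcomes, where a missing result is counted as a failure. Here both primary outcomes are continuous changes. An analyst who wants to follow section 28 has to invent the value. The natural choice is no change from baseline, but the SAP does not say so.

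The second difficulty is scope. A participant with no assessment at a visit lacks a whole questionnaire and a whole physical test, so the non-responder rule applies. The same participant is a dropout, so multiple imputation applies too. No order of priority is given, and the two methods can give different primary estimates.

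The third is fit with section 27. A repeated-measures mixed model can use incomplete records under missing at random without any filling. Single filled values enter it as if they had been measured.

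At stake are the size of both primary effects, the error rate when dropout differs between arms, and a choice of method left open until the data are in hand.

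**Working it through.** **Inputs from the SAP.** DHI: target difference 11, SD 18.95. Gait: 0.1 m/s, SD 0.15. Two-sided 5%, power 80%, dropout 24%, total 124, so 62 per arm (sections 11 and 16).

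**The plan's own figures.** n per arm = 2 × (1.960 + 0.842)² × SD² / difference².
- DHI: 2 × 7.849 × 359.10 / 121 = 46.6, so 47.
- Gait: 2 × 7.849 × 0.0225 / 0.01 = 35.3, so 36.
- Dropout: 94 / 0.76 = 123.7, so 124.

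All three reproduce. The sample size is not in error on this point.

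**Assumptions not in the SAP.** The fill is zero change and applies to every missing visit. Missingness is unrelated to outcome within each arm. Mean improvements and arm-specific dropout rates are mine, shown as ranges. Results are for one time point, by normal approximation, at two-sided 5% before any Holm adjustment. Improvement is counted as positive.

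**Formulas.** With missing share p and true mean change m in an arm:
- expected difference = (1 − p_T) m_T − (1 − p_C) m_C
- variance per arm = (1 − p) SD² + p (1 − p) m²

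**Equal dropout, true difference 11.**
- 10% missing: 0.90 × 11 = 9.90.
- 24% missing: 0.76 × 11 = 8.36. Gait: 0.76 × 0.10 = 0.076 m/s.
- DHI power at 24% is 78.9%, 76.9%, 73.7% and 69.5% for a control improvement of 0, 5, 10 and 15 points. On observed data alone (47 per arm) it is 80.3%.
- Gait power is 88.4%, 86.0% and 82.0% for a control improvement of 0, 0.05 and 0.10 m/s, against 89.8%.

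The power loss is smaller than the shrinkage because the standard error falls as well. For mean changes of 16 v 5, the variances are 319.6 and 277.5, so SE = √(597.1 / 62) = 3.10, against √(2 × 359.10 / 47) = 3.91 on observed data.

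**Unequal dropout, true difference 11.**

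| Mean change, T v C | Missing, T v C | Expected difference | Power |
|---|---|---|---|
| 16 v 5 | 30% v 18% | 0.70 × 16 − 0.82 × 5 = 7.10 | 62% |
| 16 v 5 | 18% v 30% | 0.82 × 16 − 0.70 × 5 = 9.62 | 88% |
| 21 v 10 | 30% v 18% | 0.70 × 21 − 0.82 × 10 = 6.50 | 52% |
| 21 v 10 | 14% v 34% | 0.86 × 21 − 0.66 × 10 = 11.46 | 95% |

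**No true difference.**
- Equal dropout: bias 0, rejection 5.0%.
- 30% v 18%, both arms improving 10: (0.70 − 0.82) × 10 = −1.2 points, rejection 6.8%.
- 30% v 18%, both arms improving 15: −1.8 points, rejection 8.7%. Here 8.2 points of the rejection rate favour CONTROL, and false claims for TREATMENT fall to 0.6%.
- Swapping the imbalance swaps the direction.

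**The case against.** Several points on the other side have weight.

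*The two rules may not compete.* The separate label could mean that participants missing one instrument get the fill and dropouts get multiple imputation, or that dropouts are examined in a separate analysis. Under the split, the 24% would go to multiple imputation and the figures above would overstate the effect. This stands as a possible reading, so a reader who infers an outright contradiction goes too far. But the SAP confirms neither reading, and taken literally the fill covers dropouts as well.

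*Zero change may be deliberate.* It could be a chosen cautious assumption, and then the filled value is the intended outcome. A reader might infer that the fill is invalid or can only mean zero change. The documents support only that it is undefined and unjustified.

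*Bias is not automatic.* A reader might infer bias whenever follow-up is incomplete. That is wrong: the fill gives the right mean if dropouts truly do not change, and it leaves the difference unbiased when the arms do not differ and dropout is equal and unrelated to outcome.

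*Blinding limits abuse.* Under sections 14 and 32 a blinded biostatistician analyses Group A against Group B without compliance data before the code is opened. This hinders choosing a method by direction. It does not prevent choosing by the size of the A–B difference or its p-value.

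*The planning figure is cautious.* Section 11 calls 24% conservative. At 10% missing the shrinkage is only 1.1 points, so it is not established that the fill would dominate the result.

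**Conclusion.** The concern holds as a defect of definition and priority in the primary analysis. Section 28 prescribes a fill that cannot be carried out for DHI or gait velocity without inventing a value, and names a second method of overlapping scope without ranking the two.

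Its size depends on the reading. If the fill is zero change for all missing visits, equal dropout reduces the expected effect by the missing share; at the planned 24%, both expected effects fall below the differences that section 11 calls clinically important. Unequal dropout can shrink the effect further, enlarge it, or create a modest false difference in either direction. The zero-change value, the mean improvements and the arm-specific dropout rates are assumptions. The point that the rule is undetermined needs none of them. It should be settled before the code is opened.

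**What to change.** Delete non-responder imputation as the primary handling of DHI, gait velocity and the continuous secondary outcomes. Name one primary approach valid under missing at random:

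- the mixed model on all observed visits, with baseline included as an outcome time point; or
- multiple imputation by arm, with baseline, the other visit and the other primary outcome as predictors.

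The baseline row matters in the first option. Section 27 models only 6 and 12 months, so a participant with neither visit would supply no outcome data, although section 28 promises to analyse everyone randomised.

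Use the approach not chosen as a sensitivity analysis. Add an explicitly defined zero-change or delta-adjusted scenario, so that the cautious assumption is kept and visible.

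The cost is a few sentences in the SAP and a few lines of Stata, with no new data. The downside is that the primary result then rests on missing at random, which the sensitivity analyses probe.
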